3.7.4 Data management and data cleaning

Data was checked for inconsistencies, unexpected values and missing values. If identified, these values were fed back to the data contributor (█), along with the patient identifier, for possible correction from source documents. Resubmitted, corrected, and/or transformed missing values were used to update the Data Base. If corrections could not be made, the inconsistencies and unexpected results are transformed to missing values.

Missing dates: In those cases that only the day was missing and month and year were known, in order to be able to use those dates for computing in the analysis, the date was rounded to day 15 of the month reported. Similarly, when month was not reported, the date was rounded to the sixth month of the year (June).

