2. STUDY OBJECTIVES

2.1 Primary objective(s)

The study will include patients with advanced neuroendocrine neoplasms in four different cohorts with the following primary endpoints:

Primary endpoint for cohorts 1, 2 and 3:

Nine-months clinical benefit rate (CBR) by Response Evaluation Criteria In Solid Tumors (RECIST 1.1), which is defined as the percentage of patients achieving complete response (CR), partial response (PR), or stable disease (SD) at month 9 after durvalumab plus tremelimumab was started.

Primary endpoint for cohort 4:

Nine-months overall survival rate, which is defined as the percentage of patients alive at month 9 after durvalumab plus tremelimumab was started.

Clinical Study Protocol
 Drug Substance DURVALUMAB/TREMELIMUMAB
 Study Number ESR 15-11561-61-DUNE
 EudraCT Nº: 2016-002858-20
 Edition Number: 5.0 dated on June 09th, 2021

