2.1 PRIMARY EFFICACY ANALYSES

The analysis of clinical benefit rate and overall survival rate will be performed independently for each study cohort when the last patient included in the corresponding cohort of the study will arrived to 9 months after inclusion in the study or have progressed. According to the protocol, the primary objective of the study will be based on the investigator assessment. 9-months clinical benefit rate (CBR) by Response Evaluation Criteria In Solid Tumors (RECIST version 1.1), which is defined as the percentage of patients achieving complete response (CR), partial response (PR), or stable disease (SD) at month 9 after durvalumab plus tremelimumab was started.

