2.1.1 Primary efficacy analyses in the Full Analysis Set

The primary endpoint for cohort 1, 2 and 3 is the CBR, nevertheless the result for all the cohorts will be shown below:

Table 92 Clinical benefit rate (investigator assessment) at 9 months in the Full Analysis Set

	Cohort 1	Cohort 2	Cohort 3	Cohort 4	Total
CBR at 9 months	n (% , CI 95%)				
Yes (CR, PR, SD)					
No (PD)					
Total	n (100%)				

The primary endpoint for cohort 4 is 9-months overall survival rate, which is defined as the percentage of patients alive at 9 months after durvalumab plus tremelimumab was started, nevertheless the result for all the cohorts will be shown in the following table.

Table 93 Overall survival rate at 9 months in the Full Analysis Set

	Cohort 1	Cohort 2	Cohort 3	Cohort 4	Total
Overall survival rate at 9 months	n (%), CI 95%				
Alive					
Death					
Total	n (100%)				

Concordance between investigator assessment and independent central radiology review will be analyzed using Cohen's Kappa. Although no significant differences are expected, a sensitivity analysis for the primary efficacy analysis will be performed using as response variable independent central radiology assessment.

Table 94 Agreement in CBR by Cohen's kappa coefficient in the Full Analysis Set

	Cohort 1	Cohort 2	Cohort 3	Cohort 4	Total
CBR at 9 months	Kappa k				
Investigator assessment vs. Independent review					

9-months clinical benefit rate (CBR) by Response Evaluation Criteria In Solid Tumors (RECIST version 1.1), according to independent central radiology.

Table 95 Clinical benefit rate (independent central radiology) at 9 months in the Full Analysis Set

	Cohort 1	Cohort 2	Cohort 3	Cohort 4	Total
CBR at 9 months	n (%), CI 95%				
Yes (CR, PR, SD)					
No (PD)					
Total	n (100%)				

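### Event dates known only to the year are set to June without limits, which can give survival times before first dose and can move a cohort 4 death across month 9

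*SAP*

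**What the plan says.** SAP 3.7.4 has two rules for incomplete dates. If only the day is unknown, "the date was rounded to day 15 of the month reported". If the month is unknown too, "the date was rounded to the sixth month of the year (June"). The stated purpose is general: "in order to be able to use those dates for computing in the analysis". No type of date is exempted, and no limit is set by first dose, last date known alive, last scan or data cut-off. Neither document contains another rule for partial dates.

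The same section has values checked and queried with the data contributor first, for correction from source. It then adds: "If corrections could not be made, the inconsistencies and unexpected results are transformed to missing values". It does not say whether these checks are repeated on imputed dates.

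Both primary endpoints are timed from the start of treatment. For cohort 4 the endpoint is "the percentage of patients alive at 9 months after durvalumab plus tremelimumab was started" (SAP tables section 2.1.1; Protocol 2.1 agrees). For cohorts 1 to 3 it is response or "stable disease (SD) at month 9 after durvalumab plus tremelimumab was started" (SAP tables section 2.1).

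**The concern.** An event date moved to June can be wrong by up to half a year or slightly more, while the primary endpoints are read at a single time, 9 months. Followed as written, the rule can do two things to a death or progression date known only to the year:

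- place it before first dose, giving a negative OS or PFS time;
- place it on the wrong side of month 9, in either direction, while the resulting time still looks plausible.

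The second matters most in cohort 4, where the primary outcome depends on the death date. The cohort is small and is tested with a binomial test at one-sided 5%, so a single reclassified patient can decide the result. Because the day in June is not stated, two programmers could also derive different times from the same record.

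**Working it through.** The plan gives no figure on this point to reproduce, so the check is date arithmetic followed by a simulation. Months are 30.4375 days.

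**Inputs from the documents.** The June and day-15 rules (SAP 3.7.4). Cohort 4: 33 patients, reference 9-month survival 13%, one-sided 5% (SAP 3.6). Binomial test (SAP 3.7.3). First subject in April 2017, last subject in December 2019 (Protocol 13.6).

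**Assumptions.** Exponential survival, first dose uniform over the calendar year, and a day in June from 1 to 30, because the SAP states none.

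**1. Single records, taking 15 June**

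| First dose | True death | True time (months) | Imputed date | Imputed time (months) | Effect |
|---|---|---|---|---|---|
| 3 Sep 2018 | 10 Dec 2018 | 3.2 | 15 Jun 2018 | −2.6 | negative time; still dead by month 9 |
| 5 Nov 2018 | 20 Oct 2019 | 11.5 | 15 Jun 2019 | 7.3 | alive at month 9 becomes dead |
| 1 Aug 2018 | 10 Feb 2019 | 6.3 | 15 Jun 2019 | 10.4 | dead by month 9 becomes alive |

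**2. A negative time never changes 9-month status.** If the imputed date precedes first dose, true survival is shorter than the gap between imputed and true date. The largest backward gap is from 1 June to 31 December: 213 days / 30.4375 = 7.0 months (6.5 from 15 June). This is below 9, so the patient truly died before month 9 and is still counted so.

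**3. Size among year-only deaths.** Setting S(9) = 0.13 gives a hazard of −ln(0.13)/9 = 0.227 per month. Each death date was replaced by June of its year, and survival of at least 9 months was compared before and after.

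| Day in June | Before first dose | Misclassified at 9 months | Apparent 9-month survival (true 13.0%) |
|---|---|---|---|
| 1 | 29% | 8% | 13.9% |
| 15 | 26% | 9% | 15.5% |
| 30 | 23% | 10% | 17.3% |

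For 15 June the mean error is 3.0 months and the maximum 6.5. The errors partly cancel. With 9.2% misclassified and a net shift of 15.5 − 13.0 = 2.5 points, dead-to-alive is (9.2 + 2.5)/2 = 5.9% and alive-to-dead is (9.2 − 2.5)/2 = 3.4%. The net shift favours the treatment.

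A second simulation used first doses uniform over April 2017 to December 2019 and assumed medians of 3, 6, 9 and 12 months. Over the same June days, 10–32% of dates fell before first dose and 8.7–13.5% were misclassified.

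**4. The day-15 rule.** Under the assumptions of step 3, a missing day alone misclassifies about 0.7% of such deaths, puts 2.7% before first dose and leaves apparent survival at 13.0%. The effect on 9-month status is negligible.

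**5. Scale for cohort 4.** The frequency of year-only deaths is not in the documents. If 5% of 33 patients were affected: 33 × 0.05 × 0.092 = 0.15 patients misclassified, and the cohort rate moves by 0.05 × 2.5 ≈ 0.1 point. At 10%: 33 × 0.10 × 0.092 = 0.30 patients, and about 0.25 point.

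**6. Weight of one patient.** Exact upper binomial tails for n = 33 against 13%: 9 alive gives p = 0.022, 8 alive gives p = 0.057. Against 18% (13% plus the 5% margin): 11 gives 0.025, 10 gives 0.060.

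**The case against.** The strongest objection is that this will hardly ever occur. Survival is collected every 4 weeks on treatment (Protocol schedule of assessments, footnote n). Appendices 2 and 3 mark survival contacts during follow-up more densely than the 6-monthly collection in that footnote. Date of death is a recorded variable for SAEs (Protocol 10.3), and sites are queried before any date is imputed. This largely stands: year-only death dates should be rare. Some exposure remains, because deaths clearly due to progression are not reported as SAEs (Protocol 10.3.2.1), so their dates depend on survival follow-up.

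The cleaning rule in SAP 3.7.4 is also partial protection, since a death before first dose is a plain inconsistency. But the SAP does not say that the check follows imputation. If it did, a known death would lose its date, and a plausible date on the wrong side of month 9 would still pass. Multiple imputation in SAP 3.7.5 names only the clinical benefit rate, not cohort 4's survival endpoint.

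Two stronger readings are tempting. A reader might infer that the quarter or so of dates falling before first dose also corrupts the primary endpoint; step 2 of the working shows that it cannot. A reader might also infer that all four primary analyses are equally exposed. Cohorts 1 to 3 (93 of 126 patients) take their status mainly from dated scans, so a missing month there is less likely to matter for the primary endpoint.

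**Conclusion.** The June rule is faulty as written: it is an explicit instruction without limits, and following it can give impossible event times or times on the wrong side of month 9. The two effects have different consequences. Dates before first dose (about 23–29% of year-only deaths) harm OS and PFS only. Misclassification at month 9 (about 8–10%) bears mainly on cohort 4's primary endpoint. Both figures rest on exponential survival with 13% alive at 9 months, uniform enrolment and a day from 1 to 30 June, and they apply only to deaths known to the year alone.

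The expected effect on cohort 4 is small, about 0.15–0.3 patients if 5–10% were affected, and that frequency is an illustration. The documents do not support a claim that the primary result is likely to be wrong. The rule still deserves correction because one patient can decide the binomial test and the data needed to limit the imputed date are already collected. The day-15 rule needs the same limits for consistency, not because of its size.

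**What to change.** Amend SAP 3.7.4 for event dates:

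- An imputed date may not precede the latest of first dose, last date known alive and, for progression, the last progression-free assessment. It may not follow the next known contact or data cut-off. It must stay within the reported year, or month if known.
- State the day used in June. Use the default date if it lies inside these limits, and otherwise the midpoint of the limits.
- Repeat the consistency checks after imputation and list every imputed event date.

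The cost is a few sentences in the SAP and a few lines of code. The gain depends on contact frequency. A similar rule, moving the date to the nearest limit instead of the midpoint, was simulated with medians of 6 and 12 months. It removed all times before first dose and cut misclassification from about 12–13% to 1.8% with 4-week contacts and 4.7% with 12-week contacts, but only to 9–10% with 6-month contacts. Where contacts are that far apart, the listing is the main safeguard.

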3.7.5 Missing Data

Assuming that the pattern of missingness in the primary endpoint variable (clinical benefit rate at 9 months) are missing at random (1), missing data will be treated using statistical multiple random imputation (2,3,4). Once data are collected, according to the missing data pattern observed, it should be considered if pre-specified methods are appropriate. A full reporting of all reasons for patient discontinuation should be given where possible, in order to identify the most important reasons that caused it. As suggested by the EMA (2), the seed of the pseudorandom number generator that will be used to randomly generate imputations for the missing values is pre-specified ("55881234") to avoid bias being introduced by *post hoc* selection of the seed and therefore the random numbers to be imputed.

3.7.6 Interim Analyses

Not applicable

3.7.7 Data Monitoring

The sponsor's or representative (e.g., CRO's CRA) will maintain contact with the investigator and designated staff by telephone, and/or letter, and/or email between study visits. Monitoring visits to each investigational site will be conducted by the assigned CRA as described in the monitoring plan. The investigator (if regionally required, the heads of the medical institutions) will allow the CRA to inspect the clinical, laboratory, and pharmacy facilities to assure compliance with Good Clinical Practices and local regulatory requirements. The eCRFs and subject's corresponding original medical records (source documents) are to be fully available for review by the sponsor's representatives at regular intervals. These reviews verify adherence to the study protocol and data accuracy in accordance with federal regulations. All records at the investigational site, including source documents, are subject to inspection by the regulatory authorities and to review by the Ethical Committee.

3.7.8 SUMMARY OF STUDY DATA

All continuous variables will be summarised using the following descriptive statistics: n (non-missing sample size), mean, standard deviation, median, maximum and minimum. The frequency and percentages (based on the non-missing sample size) of observed levels will be reported for all categorical measures. Frequency counts and percentage of subjects within each category will be provided for categorical data. Ninety-five (95) percent confidence intervals (95% CI) may also be presented, as appropriate. In general, all data will be listed, sorted by site, treatment and subject, and when appropriate by visit number within subject. All summary tables will be structured with a column for each cohort in the order (cohort 1, 2, 3 and 4) and will be annotated with the total population size relevant to that table/treatment, including any missing observations.

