1.4.1.3 Durvalumab + tremelimumab

The preclinical and clinical justification for this combination as noted in Section 1.1.4 also supports the synergy of this combination. Available data, such as those presented by Wolchok et al, suggest that the combination of agents targeting PD-1/PD-L1 and CTLA-4 may have profound and durable benefits in patients with melanoma (Wolchok et al 2013). Of the 102 subjects with advanced NSCLC treated with durvalumab in combination with tremelimumab in Study D4190C00006, 63 subjects with at least 16 weeks of follow-up were evaluable for response (defined as measurable disease at baseline and at least 1 follow-up scan; this included discontinuations due to disease progression or death without follow-up scan). Of the 63 evaluable subjects, 17 (27%) had a best overall response of PR, 14 (22%) had SD, 22 (35%) had PD, and 10 (16%) were not evaluable. The ORR(confirmed and unconfirmed CR or PR) was 27% and the DCR (CR, PR, or SD) was 49% as assessed by RECIST v1.1.

Current experience with single-agent IMT studies suggests that clinical responses may be restricted to a subset of any given patient population and that it might be beneficial to enrich the patient population by selecting patients likely to respond to therapy. To date, no assay has been established or validated, and no single approach has proven accurate, for patient enrichment for IMTs. However, independent data from multiple sources using different assays and scoring methods suggests that PD-L1 expression on tumor cells and/or tumor infiltrating cells may be associated with greater clinical benefit.

Data from ongoing studies with durvalumab and other agents targeting the PD-1/PD-L1 pathway suggest, as shown in a number of tumor types (eg, NSCLC, renal cell carcinoma, and melanoma), that monotherapy may be more efficacious (in terms of ORR) in patients who are PD-L1-positive.

Given these findings, a number of ongoing studies are assessing the activity of agents in patients with PD-L1-positive tumors. There is also an unmet medical need in patients with PD-L1-negative tumors that needs to be addressed. Data, as of 27 January 2015 from Study 006 show that with the addition of tremelimumab to durvalumab, the ORR can be increased to 25% in patients with PD-L1 negative NSCLC.

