Evaluation	Time Since Last Dose							
	Day (±3)	Months (±1 week)						12 Months and every 6 Months (±2 weeks)
		30	2	3	4	6	8	
Physical examination ^a	x							
Vital signs (temperature, respiratory rate, blood, pressure, pulse)	x							

Clinical Study Protocol
 Drug Substance DURVALUMAB/TREMELIMUMAB
 Study Number ESR 15-11561-61-DUNE
 EudraCT N°: 2016-002858-20
 Edition Number: 5.0 dated on June 09th, 2021

Weight	x							
AE/SAE assessment	x	x	x					
Concomitant medications	x	x	x					
Palliative radiotherapy	As clinically indicated							
ECOG performance status ^b	x	x	x					
Subsequent anti/cancer therapy	x	x	x	x	x	x	x	x
Survival status: phone contact with subjects who refuse to return for evaluations and agree to be contacted		x	x	x	x	x	x	x (every 2 months)
Urine hCG or serum β hCG	x							
Hematology	x	x	x					
Serum chemistry	x	x	x					
Thyroid function tests (TSH, and fT3 and fT4) ^c			x					
Pharmacokinetic assessment, if applicable			x					
SPD-L1 concentration (to assess target engagement)			x					
Tumour assessment (CT or MRI)	
For subjects who continue on MEDI4736 post-confirmed progression at the investigator's discretion (following consultation with the sponsor), tumour assessments should be performed relative to the date of first infusion per SCHEDULE OF STUDY ASSESSMENTS until study drug is stopped.
 
For subjects who discontinue study drug following confirmed progression, scans should be conducted according to local clinical practice until a new treatment is started (these scans are optional).
							

^a Full physical exam

^b PS to be collected if available at the 2 monthly calls to obtain subsequent anti/cancer therapy and survival status

^c Free T3 and free T4 will only be measured if TSH is abnormal. They should also be measured if there is clinical suspicion of an adverse event related to the endocrine system.

^d For patient questionnaires different approaches based on indication and study design.

Clinical Study Protocol
Drug Substance DURVALUMAB/TREMELIMUMAB
Study Number ESR 15-11561-61-DUNE
EudraCT Nº: 2016-002858-20
Edition Number: 5.0 dated on June 09th, 2021

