3.7 DATA ANALYSIS

3.7.1 Analysis Sets

The analysis sets will be defined as follows:

- **Full Analysis Set** will include all allocated subjects. This will be primary analysis set for the efficacy endpoints.
- **Per Protocol Analysis Set** will include those subjects who were allocated and received at least one dose of the assigned study drug and had no major protocol deviations. The subjects will complete both baseline and at least one post-baseline tumor assessments (week 12).
- **Safety Analysis Set** will include all subjects who were allocated and received at least one dose of the study drug and had at least one post-baseline safety evaluation (week 12). This will be the analysis set for all safety evaluations.
- **Pharmacodynamic Analysis Set:** All the subjects who have received at least one dose of study drug and have evaluable pharmacodynamic data.

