2.2.1 Overall response rate (ORR)

The Overall response rate (ORR) by irRECIST and the duration of the response is shown in the following tables for the Full Analysis Set:

Table 100 ORR in the Full Analysis Set

	Cohort 1	Cohort 2	Cohort 3	Cohort 4	Total
ORR	n (%, CI 95%)				
CR					
PR					
SD					
PD					
Total	n (100%)				
CR or PR					
SD or PD					
Total	n (100%)				

Table 101 Duration of the response in the Full Analysis Set

Duration of the response (months)	n	Mean (SD)	Median (IQR)	Min-Max	95% CI of the mean
Cohort 1					
Cohort 2					
Cohort 3					
Cohort 4					
Total					

The Overall response rate (ORR) by irRECIST and the duration of the response is shown in the following table for the Per Protocol Analysis Set:

Table 102 ORR in the Per Protocol Analysis Set

	Cohort 1	Cohort 2	Cohort 3	Cohort 4	Total
ORR	n (%), CI 95%				
CR					
PR					
SD					
PD					
Total	n (100%)				
CR or PR					
SD or PD					
Total	n (100%)				

Table 103 Duration of the response in the Per Protocol Analysis Set

Duration of the response (months)	n	Mean (SD)	Median (IQR)	Min-Max	95% CI of the mean
Cohort 1					
Cohort 2					
Cohort 3					
Cohort 4					
Total					

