2.2.2 Response status at 6 and 12 months

The response status according to irRECIST at 6 and 12 months after start of study treatment is shown in the following tables for the Full Analysis Set:

Table 104 Response status at 6 months in the Full Analysis Set

	Cohort 1	Cohort 2	Cohort 3	Cohort 4	Total
Response at 6 months	n (%), CI 95%				
CR					
PR					
SD					
PD					
Total	n (100%)				
CR or PR					
SD or PD					

Statistical Analysis Plan
 Drug Substance DURVALUMAB/TREMELIMUMAB
 Study Number ESR 15-11561-DUNE
 EudraCT Nº: 2016-002858-20
 Version Number: 1.1 dated on 30/NOV/2017

Total	n (100%)				
-------	----------	----------	----------	----------	----------

Table 105 Response status at 12 months in the Full Analysis Set

	Cohort 1	Cohort 2	Cohort 3	Cohort 4	Total
Response at 12 months	n (%), CI 95%				
CR					
PR					
SD					
PD					
Total	n (100%)				
CR or PR					
SD or PD					
Total	n (100%)				

The response status according to irRECIST at 6 and 12 months after start of study treatment is shown in the following tables in the Per Protocol Analysis Set:

Table 106 Response status at 6 months in the Per Protocol Analysis Set

	Cohort 1	Cohort 2	Cohort 3	Cohort 4	Total
Response at 6 months	n (%), CI 95%				
CR					
PR					

Statistical Analysis Plan
 Drug Substance DURVALUMAB/TREMELIMUMAB
 Study Number ESR 15-11561-DUNE
 EudraCT Nº: 2016-002858-20
 Version Number: 1.1 dated on 30/NOV/2017

SD					
PD					
Total	n (100%)				
CR or PR					
SD or PD					
Total	n (100%)				

Table 107 Response status at 12 months in the Per Protocol Analysis Set

	Cohort 1	Cohort 2	Cohort 3	Cohort 4	Total
Response at 12 months	n (%, CI 95%)				
CR					
PR					
SD					
PD					
Total	n (100%)				
CR or PR					
SD or PD					
Total	n (100%)				

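### The Full Analysis Set tables for ORR and for response status at 6 and 12 months use a non-missing denominator with no place for unassessed or dead patients, so the rates are biased upward

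*SAP*

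**What the plan says.** SAP 3.7.8 states: "The frequency and percentages (based on the non-missing sample size) of observed levels will be reported for all categorical measures". It adds that summary tables "will be annotated with the total population size relevant to that table/treatment, including any missing observations".

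SAP 3.7.1 defines the Full Analysis Set differently: it "will include all allocated subjects. This will be primary analysis set for the efficacy endpoints".

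SAP 2.2.1 introduces Table 100: "The Overall response rate (ORR) by irRECIST and the duration of the response is shown in the following tables for the Full Analysis Set". SAP 2.2.2 introduces Tables 104 to 107: "The response status according to irRECIST at 6 and 12 months after start of study treatment is shown in the following tables". Each of these response tables lists CR, PR, SD and PD, closes at 100%, and then splits patients into CR or PR against SD or PD. None has a row for not evaluable, missing or dead, although NE is in the SAP's abbreviation list. (Tables 101 and 103 report duration of response and are not part of this point.)

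The missing-data section, SAP 3.7.5, is written for the primary endpoint. It assumes that "the pattern of missingness in the primary endpoint variable (clinical benefit rate at 9 months) are missing at random" and imputes on that basis. The rule in SAP 3.7.3 that keeps lost or discontinued patients who have at least one tumour evaluation also names only the primary endpoint.

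On scanning after progression, Protocol Appendix 3 says that for patients who stop drug after confirmed progression, "scans should be conducted according to local clinical practice until a new treatment is started (these scans are optional").

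**The concern.** A patient with no recorded response has no cell in these tables, and 3.7.8 then removes that patient from the percentage. Patients without a record are likely to be mostly treatment failures: deaths before the first scan for ORR, and deaths or earlier progressions at 6 and 12 months. The published figure would be a response rate among patients still being assessed, under a Full Analysis Set label.

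The per-protocol set already requires a post-baseline tumour assessment. If the Full Analysis Set ORR also rests only on assessed patients, the two analyses nearly coincide on this point, and the primary set loses most of its purpose for ORR. ORR is the first secondary objective listed, and the protocol says the results will inform strategic decisions about further development.

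**Working it through.** **No stated figure to reproduce.** The documents give no ORR, no time-point response rate and no non-evaluable rate. The allocated numbers are consistent: 28 × 1.10 = 30.8, taken as 31; 30 × 1.10 = 33; 3 × 31 + 33 = 126.

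**Direction.** With k responders, N allocated and n with a recorded response, the plan reports k/n where the Full Analysis Set rate is k/N. The ratio is N/n, above 1 whenever k > 0 and any allocated patient lacks a record. This needs no further assumption.

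**Size.** The number recorded has to be assumed. I put an exponential curve through the planning rates in SAP 3.6, S(t) = S9^(t/9), with t in months (12 weeks = 84/30.4375 = 2.76; 8 weeks = 56/30.4375 = 1.84).

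*Cohort 4, ORR, deaths before the first scan.* S9 is 13% (reference) or 13% + 10% = 23% (expected). SAP 3.7.2 puts the first scan at week 12; SAP 3.5 and its Table 1 scan every 8 weeks.

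| First scan | S9 | Alive at scan | Of 33 | N/n |
|---|---|---|---|---|
| Week 12 | 13% | 0.535 | 17.7 | 1.87 |
| Week 12 | 23% | 0.637 | 21.0 | 1.57 |
| Week 8 | 13% | 0.659 | 21.7 | 1.52 |
| Week 8 | 23% | 0.740 | 24.4 | 1.35 |

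With a hypothetical 3 responders, 3/33 = 9.1% would be shown as 3/21 = 14.3% or 3/18 = 16.7% with the week-12 scan.

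*Cohorts 1 to 3, status at 12 months, if progression is not carried forward.* The progression-free rate at 9 months is 30% (reference) or 50% (expected).

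- Reference: 0.30^(12/9) = 0.201, about 6 of 31; N/n = 1/0.201 = 4.98.
- Expected: 0.50^(12/9) = 0.397, about 12 of 31; N/n = 1/0.397 = 2.52.

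A hypothetical 3 responders are 3/31 = 9.7% of the cohort. The table would show 3/12 = 25% to 3/6 = 50%.

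*Cohorts 1 to 3, status at 6 months, same condition.* 0.30^(6/9) = 0.448 and 0.50^(6/9) = 0.630, so N/n is 2.23 or 1.59.

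*Cohort 4, status at 6 and 12 months, deaths alone.* The plan has no progression rate for this cohort. Survival is 0.257 or 0.375 at 6 months (N/n 3.9 or 2.7) and 0.066 or 0.141 at 12 months (N/n 15.2 or 7.1).

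**The case against.** The best defence is that the SAP never codes a death or an earlier progression as missing. The tables are labelled Full Analysis Set, and the footnote restricting percentages to patients with available data appears under baseline and study-medication tables but not under Tables 100 to 107. A programmer might carry progression forward unprompted. This stands as far as it goes: the 6- and 12-month effect is conditional on that choice. But 3.7.8 covers all categorical measures, and nothing written overrides it for these tables.

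Second, counts are shown, tables carry the total population, data are generally listed, and PFS and OS are reported separately in the Full Analysis Set. A reader could recompute the rate. That lowers the severity, but the printed percentage stays as it is.

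Third, a reader might infer that everyone who stops scanning leaves the ORR denominator. That goes too far. SAP 2.2.1 does not say when response is taken, but if ORR is a best response, one post-baseline assessment keeps the patient in. Protocol Appendix 2 also continues 12-weekly scans after a toxicity stop, and Appendix 3 keeps scheduled scans for patients treated beyond progression.

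Fourth, a reader might set the rates against the protocol's lung cancer figures for this combination, in which "17 (27%) had a best overall response of PR, 14 (22%) had SD, 22 (35%) had PD, and 10 (16%) were not evaluable". Those percentages do keep the 10 non-evaluable patients. However, the 63 are a response-evaluable subset of 102 treated patients with a different tumour, assessed by RECIST 1.1 with unconfirmed responses counted. Changing the denominator here would not make the two comparable.

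**Conclusion.** The point holds as a conflict between the 3.7.8 denominator and the all-allocated Full Analysis Set, with a certain upward direction and an unknown size. For ORR it affects only patients with no post-baseline assessment. For 6 and 12 months it affects those who died or stopped scanning after progression, unless progression or death is carried forward.

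The fold figures are upper bounds for the mechanisms they model. For cohort 4 ORR, a constant hazard from day 1 ignores the eligibility requirement of at least 12 weeks' life expectancy, which would lower early deaths. Other patients who never had a scan would add to the effect, but the documents give no rate for them. For cohorts 1 to 3, 2.5- to 5-fold assumes that no progressed patient has a recorded status at 12 months. A contrast such as 50% against 9.7% is one end of that range with an invented responder count, and should not be read as a forecast.

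A reader might also conclude that cohort 4 is worst affected. Comparing reference with reference and expected with expected, the planning rates point that way, but it is an inference from those rates and the exponential shape; the documents do not say it.

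The endpoints are secondary and descriptive, with no test or decision rule attached, and neither primary endpoint is affected. This should be fixed; it is not critical to the trial's main conclusion.

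**What to change.** In SAP 2.2.1 and 2.2.2:

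- Set the denominator of Tables 100, 104 and 105 to all Full Analysis Set patients in the cohort, and exempt these tables from the non-missing rule in 3.7.8.
- Add rows for not evaluable or missing, and for death before assessment.
- State that progression recorded earlier is carried forward to later time points.
- Define the complement of response as not CR or PR, in place of SD or PD.
- Treat Tables 106 and 107 the same way within the per-protocol set. Table 102 is largely unaffected, because that set requires a post-baseline assessment.
- Report the evaluable-only rate as a labelled sensitivity analysis.

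The 8-week and 12-week scan intervals within the SAP also need to be reconciled, since the first scan determines who counts as unassessed.

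The cost is SAP wording and additional shell rows; no new data are needed. The drawback is that the reported rates become less favourable.
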